According to Bennet et al. (2009), a 14% decrease in quality of life since baseline is considered clinically significant (Bennett, Bushmakin, Cappelleri, Zlateva, & Sadosky, 2009). Evaluated in a cohort study of 10 patients (Hackshaw et al., 2016) the interest of a 37% improvement in quality of life following lifestyle coaching by nurses, physiotherapists and adapted physical activity teachers, encourages us to propose personalised coaching with a physical activity adapted to the patient and specific to her pathology. We believe that this solution would allow for adaptation to the patient's choice of physical activities, but would also allow for better individualised follow-up and better adaptation to the patient's physical and organisational constraints, with a better medium and long-term impact on quality of life.

We hypothesize an improvement in the quality of life of fibromyalgia patients in the medium (6 months) and long term (12 months) thanks to personalized coaching (specific physical activity).

The objective of our study is to compare the impact of two physical activity management in fibromyalgia patients at 6 and 12 months:

- 1. Control group: Traditional non-specific management in a common "multipathology" group, with activity trackers**
- 2. Experimental group: Specific management in a "fibromyalgia patients" group, with activity trackers**

1.2. *BENEFITS AND RISKS FOR RESEARCH PARTICIPANTS*

Benefits

Individual benefit

Physical activity improves pain, quality of life and body mass quality of patients.

We expect this innovative health sport coaching to optimise these improvements (in quality of life, pain and body mass quality) compared to standard patient management.

Collective benefit

- This new treatment modality will improve the care available to the algologist for the treatment of his patients.

- We also wanted to evaluate a new, simple and rapid test of kinesiophobia using isochrony between an imagined movement and an executed movement to predict a patient's adherence to physical activity management. If this test is effective, it will allow better targeting of patients who can benefit from a rehabilitation programme using physical activity coaching.
- Finally, an evaluation of an innovative patient monitoring with impedancemetry should make it possible to propose new monitoring tools for evaluating patients with fibromyalgia.

Risks

No excess risk due to participation in the study is expected

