Evaluating the isochrony between a physically performed and mentally simulated movement as a predictive test of improved quality of life following a physical activity programme Isochrony will be assessed by the difference between the duration of the performed movement and the imagined movement of taking a review on a table at D0. The quality of life of the patients will be assessed from the FIQR score at M6 and M12.

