3.2. INCLUSION CRITERIA

- Patient of legal age,
- Diagnosis of fibromyalgia (Häuser et al., 2017):

$4 < \text{WPI} < 6$ and $\text{SSS} \geq 9$ **OR**

$\text{WPI} \geq 6$ and $\text{SSS} \geq 5$ **AND**

pain present in **at least 4** of the 5 regions of the body (5 regions = 4 dials + the axis).

- Patient with FIQR $\leq 59/100$
- Patient can be followed for 12 months in the CETD,
- Patient able to follow the physical activities proposed by "Siel Bleu", on a physical and organisational level,
- Patient with a smartphone and/or computer (mac/pc) with an internet connection allowing the use of a monitoring application linked to the activity tracker,
- Patient with the ability to understand the protocol and who has given consent to participate in the study,
- Patient with social security coverage.

3.3. *NON-INCLUSION CRITERIA*

- Patient participating in an interventional trial within 3 months of inclusion,
- Pregnant or breastfeeding women, or women with the potential to conceive without effective contraception,
- Patient who is a minor, under guardianship, curatorship or deprived of liberty,
- Patient unable to follow the protocol, as judged by the investigator, or unwilling to use the digital applications,
- Patients with contraindications to physical activity,
- Patients who have already taken part in the physical activities offered by "Siel Bleu".

3.4. *FEASIBILITY*

An investigation with the CETD-Vendée team, cross-checked with the files of the "Siel Bleu" association network, showed an active file of 4 new patients per week on average, i.e. 200 new patients per year.

The Nantes University Hospital estimated that it would be possible to include an active file of 24 patients per year, given their patient base and the resources required for this project.

With a 20% refusal rate, we would have 179 patients included in the year.

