All variables will be described globally and by group. The description will include the numbers and percentages of modalities for qualitative variables and the minimum, maximum, mean, standard deviation and median for quantitative variables.

Main criterion

The patients' quality of life will be measured using the FIQR questionnaire at D0, M6 and M12. The evolution of the score at 6 and 12 months will be characterised by a graph and compared between the 2 groups using a linear regression model taking into account the baseline score at D0, the time effect, the "time*group" interaction and the repeated nature of the data.

The comparison of the evolution of the score at M6 will be tested from the M6 contrast.

Secondary criteria

The evolution of pain will be graphically characterised and compared using a mixed linear regression model taking into account the baseline data of the D0 score and the repeated nature of the data.

Neuropathic pain will be assessed using the DN4 questionnaire score. It will be compared between the two groups using a mixed generalized linear regression model taking into account the repeated nature of the data.

The evolution of the isochrony will be characterised graphically and compared using a mixed linear regression model taking into account the baseline data J0 and the repeated nature of the data.

The evolution of anxiety will be assessed from the total HAD score and compared between the two groups using a mixed linear regression model taking into account the baseline D0 score and the repeated nature of the data.

The evolution of pain on muscle compression will be assessed from the total WPI score and compared between the two groups using a mixed linear regression model taking into account the baseline score on D0 and the repeated nature of the data.

The severity of symptoms will be measured from the SSS score and compared using a mixed linear regression model taking into account the baseline data of the D0 score and the repeated nature of the data.

Physical activity monitoring will be collected every month until M12. Each month, the percentage of goal achievement will be calculated. The average percentage of success will be plotted and compared between the 2 groups using a mixed linear regression model taking into account the repeated nature of the data.

The evolution of lean body mass will be collected at D0 M6 and M12 and compared using a mixed linear regression model taking into account the repeated nature of the data.

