
The evolution of kinesiophobia will be assessed using the TAMPA self questionnaire at D0, M6 and M12. The total score will be compared between the groups using a mixed linear regression model taking into account the baseline score on D0 and the repeated nature of the data.

The evolution of the quality of life will be measured using the EQ5D-5L questionnaire at D0, M6 and M12. The evolution of the score will be characterised by a graph and compared between the 2 groups using a mixed linear regression model taking into account the baseline score on D0 and the repeated nature of the data.

Exploratory criterion

The evolution of the FIQR score will be evaluated using a linear mixed model taking into account the group and repeated nature of the data as well as the isochrony data at D0 in order to evaluate its predictive character.

Statistical justification of the number of inclusions

The study is a superiority trial on the decrease of the FIQR score (improvement of the quality of life) at 6 months between a control group (classic non-specific management in a common "multipathology" group) and an experimental group (specific management in a "fibromyalgia patients" group).

According to Hackshaw et al. (2016), the mean baseline QoL of the ten patients included was 49.4 (13.8) on the FIQR scale. After 6 months of intervention (life coaching including physical activity), the mean level of quality of life was 31.0 (13.2), i.e. a decrease in score of 18.4 points (37% decrease).

Evidence of a 7-point difference between the two intervention groups at M6 will be considered clinically significant.

With a power of 80%, and an alpha risk of 5%, 114 patients will be needed to show this difference. To ensure the necessary power, an additional 10% of patients will be included, for a total of 126 patients.

Expected level of statistical significance

The alpha risk is set at 5%.

Statistical criteria for stopping the research

NA

Method of accounting for missing, unused or invalid data

All missing data and the reason for it will be described in each group.

The FIQR score will be estimated and compared between the 2 groups using a linear model taking into account the repeated nature of the data, so no imputation method will be applied.

Managing changes to the original strategy analysis plan

NA

Selection of persons to be included in the analyses

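### The exploratory isochrony model omits the D0 FIQR score, so it cannot separate predicting improvement from marking severity at entry (minor; a free improvement)

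*Combined protocol and SAP*

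**What the plan says.** Section 2.2 (exploratory secondary objective) proposes D0 isochrony "as a predictive test of improved quality of life following a physical activity programme". Isochrony is the difference in duration between the performed and the imagined movement. For the outcome it adds: "The quality of life of the patients will be assessed from the FIQR score at M6 and M12".

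Section 5.2 (exploratory criterion) gives the analysis in one sentence. It opens with outcome and method: "The evolution of the FIQR score will be evaluated using a linear mixed model". Its remaining words, apart from the stated purpose, are the list of model terms: "taking into account the group and repeated nature of the data as well as the isochrony data at D0". No D0 FIQR covariate, time effect or isochrony-by-time term is named, and no other section adds one to this model.

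The primary model, for the same questionnaire, is written out more fully: "taking into account the baseline score at D0, the time effect", followed by the time-by-group interaction. Of the ten secondary analyses in section 5.2, seven name the D0 value (pain, isochrony, HAD, WPI, SSS, Tampa, EQ5D-5L). Three do not (DN4, activity-tracker goals, lean mass).

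**The concern.** The objective is about improvement, but the listed terms describe FIQR level. If patients with more disturbed isochrony also tend to have higher FIQR at entry, they will tend to have higher FIQR later, because FIQR is correlated with itself over time. The isochrony coefficient is then non-zero even when isochrony says nothing about who improves.

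At stake is the conclusion of the only analysis specified for this objective. It could report a predictor of improvement that is only a marker of severity at D0. The term that answers the question is also left to be chosen at the analysis stage.

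**Working it through.** **1. What the isochrony effect means under each reading of the outcome.**

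- *M6 and M12 as outcomes* (section 2.2). The effect is mixed with D0 severity because D0 FIQR is not adjusted for. An isochrony-by-time term would not cure this, since it would only compare M6 with M12.
- *D0, M6 and M12 as outcomes.* The effect is mixed with D0 severity because D0 FIQR is part of the averaged outcome and no isochrony-by-time term separates later visits from D0.
- *Change from D0 as outcome* (the sense of evolution in the primary endpoint, section 2.1). Suppose follow-up FIQR depends on isochrony only through D0 FIQR, with slope r. If D0 FIQR has slope b on isochrony, change has slope (r − 1)·b. For r below 1 and b not zero, this is regression to the mean, not prediction beyond the D0 score.

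**2. The plan's own figure.** The documents give no figure for the exploratory analysis. The number of patients used here, 114, is the sample size in section 5.2. With a 7-point difference, SD 13.2 (the cited pilot's 6-month SD; the plan does not label its planning SD), two-sided 5% and 80% power, n per arm = 2 × (1.96 + 0.84)² × 13.2² / 7² ≈ 56, or 112 in total. The t-based calculation gives 57 per arm, 114 in total. The figure reproduces, and the point does not depend on it.

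**3. Inputs for the size.**

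- From the documents: 114 patients, and entry limited by "Patient with FIQR" at most 59 out of 100 (section 3.2). For the D0 distribution, "the mean baseline QoL of the ten patients included was 49.4 (13.8) on the FIQR scale".
- Assumed: correlation a between isochrony and D0 FIQR of 0 to 0.4; correlation r between D0 and M6 FIQR of 0.3 to 0.7; normal D0 scores; complete data; two-sided 5% test with group in the model.
- Null: isochrony has no value beyond D0 FIQR.

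**4. Effect of the entry cap.** The cap lies at k = (59 − 49.4)/13.8 = 0.696 SD above the mean. With λ = φ(k)/Φ(k) = 0.414, the retained variance is 1 − 0.696 × 0.414 − 0.414² = 0.541, so the SD ratio is u = 0.735. A correlation c becomes c·u / √(1 − c² + c²u²):

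- a = 0.1, 0.2, 0.3, 0.4 become 0.074, 0.148, 0.225, 0.306
- r = 0.3, 0.5, 0.7 become 0.225, 0.391, 0.585

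**5. Rate at which the listed model declares isochrony predictive at M6.** Under this null the isochrony–M6 correlation is ρ = a′ × r′ (capped values). The test is a noncentral t with 111 degrees of freedom and noncentrality ρ√114 / √(1 − ρ²). At the top corner ρ = 0.306 × 0.585 = 0.179 and the noncentrality is about 1.94, which gives about 48%.

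| a | r = 0.3 | r = 0.5 | r = 0.7 |
|---|---|---|---|
| 0 | 5% | 5% | 5% |
| 0.1 | 5% | 6% | 7% |
| 0.2 | 6% | 9% | 15% |
| 0.3 | 8% | 16% | 29% |
| 0.4 | 11% | 25% | 48% |

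Simulation with 6,000 trials per cell agrees to within simulation error. With D0 FIQR added as a covariate, the rate is about 5% in every cell, because under this null nothing remains for isochrony to explain.

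**The case against.** **Shorthand.** Only the primary model is written out in full; no secondary model names a time effect or a time-by-group term. The exploratory sentence may therefore mean the primary model plus D0 isochrony. That is plausible, and it makes this a gap in wording rather than proof that a wrong analysis will be run. It does not close the gap: seven secondary models name their baseline in equally short sentences, and nothing in the documents adds D0 FIQR or a contrast to this model.

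**Evolution means change from D0.** The primary endpoint uses the word that way, so the reading is natural. Mixing with D0 level then gives way to regression to the mean, as shown in the working. D0 FIQR is still needed if the question is prediction beyond the starting score.

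**Adjustment is not a complete answer.** If a single D0 FIQR is a noisy measure of stable severity and isochrony tracks that severity, the adjusted isochrony effect will be non-zero although isochrony is unrelated to change. A reader might infer that the adjusted model is then in error. It is not: in that setting isochrony does add information beyond the recorded D0 score. Likewise, an association with change that arises from regression to the mean is a true answer to a different question. Neither should be counted as a false positive here.

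**The size is assumed.** This stands. At correlations of 0.1 to 0.2 most cells are close to 5%, and at zero the problem disappears.

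**Conclusion.** The point holds as a minor one. The exploratory model as listed cannot tell prediction of improvement from severity at D0. Under the stated assumptions it declares isochrony predictive at M6 in about 5% to 48% of trials when isochrony adds nothing beyond D0 FIQR, against about 5% with the baseline score included. The range rests on two correlations that the documents do not give and on a D0 distribution taken from a ten-patient pilot.

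Three stronger readings are tempting and are not supported:

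- That the trial's main results are at risk. The primary model names D0 FIQR, and this sentence does not enter any between-arm comparison.
- That patients would be wrongly selected for treatment. Section 1.2 ties the targeting aim to predicting "adherence to physical activity management. If this test is effective, it will allow better targeting of patients who can benefit", which concerns adherence and not this FIQR model.
- That a false finding is likely. That depends on a fairly strong isochrony–FIQR correlation, for which there is no evidence in the documents either way.

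**What to change.** In section 5.2, state the exploratory model as follows: FIQR at M6 and M12 as outcomes; D0 FIQR, group, time, D0 isochrony and isochrony-by-time as terms; repeated measures accounted for within patient. The isochrony-by-time term serves only to give separate estimates at M6 and M12.

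Name the isochrony effect at M6 and at M12 as the test of whether isochrony adds predictive information beyond the D0 score, and report it in those words. An analysis of change from D0 is optional. If it is included, say that it answers a different question.

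The cost is two or three sentences. FIQR is already collected at D0, M6 and M12, so no visit, measurement or patient is added.

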4.2. GENERAL RESEARCH METHODOLOGY

The research has the following characteristics:

- Open study,
- Multicentric (CHD Vendée, CHU Nantes),
- Controlled,
- Of superiority,
- Randomised

Duration of inclusion: 18 months

Duration of participation: 12 months (*including 6 months of adapted physical activity depending on the randomisation arm*)

Duration of the research: 30 months

Randomisation arm :

- **Control group: Classic non-specific management in a common "multipathology" group, with activity trackers:**
 - One face-to-face session per week with the "Siel Bleu" association in the different sites of the Vendée and Loire-Atlantique.
- **Experimental group: Specific telephone coaching for fibromyalgia patients, with activity trackers:**
 - A one-hour face-to-face individual session conducted by the "Siel Bleu" association - Eight telephone coaching sessions in Physical Activity - Health :

- Four 30-minute sessions by the "Siel Bleu" association
- Four 30-minute sessions by physiotherapists from participating institutions

The nine sessions will be spread over 6 months.

Concerning the continuation of physical activity after the end of the experiment (i.e. after M6), the physical activity coaching service could be provided, if the patient so wishes and on his or her initiative, by a private physiotherapist or an adapted physical activity teacher from "Siel Bleu". Similarly, standard care is based on an existing activity currently offered by "Siel Bleu" and can therefore be integrated by the patient who so requests.

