The main analysis will be performed on the Intent-to-Treat (ITT) population, i.e. on all randomised patients. A sensitivity analysis will be performed on the Per Protocol (PP) population including randomised patients for whom no major protocol deviations were identified.

A data review meeting will be held to review and define the major criterion or not for each of the deviations.

Randomisation

Randomisation will be carried out in a 1:1 ratio and will be done in blocks.

Randomisation will be carried out in Ennov Clinical by connecting to the website: <https://www.dirc-hugo-online.org/csonline/>. The connection will be made through a login, a password and a study number, delivered by the data manager of the Research Unit of the La Roche sur Yon Hospital. The following information must be filled in:

- First initial of the name,
- First initial of the first name,
- Month and Year of birth,
- Compliance with inclusion and non-inclusion criteria (yes/no),

Randomisation will be carried out by the investigator after confirmation of the possibility of inclusion in the study. The inclusion number will be assigned automatically during randomisation.

An email confirmation will be sent to the person who performed the randomisation and to all persons involved.

The randomisation list will be carried out by the statistician of the Research Unit of the CHD of La Roche sur Yon. An explanatory guide to randomisation will be available online in Ennov Clinical

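### Centre is neither a described stratification factor nor a term in any planned model, so a chance centre imbalance would go uncorrected; the cost is a little precision, not bias

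*Combined protocol and SAP*

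**What the plan says.** Section 4.2 lists the trial as open, randomised and "Multicentric (CHD Vendée, CHU Nantes"). Section 4.1 has the clinical assessments done by the pain-centre teams at four sites: three in Vendée, plus Nantes.

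On allocation, section 5.2 (Randomisation) states: "Randomisation will be carried out in a 1:1 ratio and will be done in blocks". It gives no block length and no stratification factor, and it speaks of the randomisation list in the singular. The required entry fields are the patient's initials, month and year of birth, and an eligibility confirmation. Centre is not one of them.

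On analysis, section 5.2 (Main criterion) gives the primary FIQR model baseline score, time, the time-by-group interaction and a repeated-measures structure. The secondary and exploratory models follow the same pattern. None names centre.

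On intake, section 3.4 expects 200 new patients per year in Vendée. For Nantes, "it would be possible to include an active file of 24 patients per year".

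On delivery, section 4.2 gives the experimental arm nine sessions, including "Four 30-minute sessions by physiotherapists from participating institutions". The Siel Bleu association gives the other five and runs all the control sessions.

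**The concern.** Centre is known before randomisation and can be related to outcome through case-mix, assessors or local delivery. A multicentre plan normally either balances allocation on it, adjusts for it, or does both. As written, this plan does neither.

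Two things follow. If the smaller centre happens to fall unevenly between the arms, part of any centre difference in FIQR is carried into the estimated treatment effect for that trial. And whether or not an imbalance occurs, centre variation stays in the residual and slightly widens the confidence interval.

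There is also a reporting issue. If centre is first considered once the data are in hand, the team must choose between adjusted and unadjusted results after seeing them. Section 5.2 marks the handling of changes to the analysis strategy as not applicable, so nothing governs that choice.

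**Working it through.** **1. Reproduce the planned sample size.** The plan says "With a power of 80%, and an alpha risk of 5%, 114 patients will be needed to show this difference", and "Evidence of a 7-point difference between the two intervention groups at M6 will be considered clinically significant". It does not state which SD was used or whether alpha is two-sided. The pilot study's 6-month result, "the mean level of quality of life was 31.0 (13.2"), supplies an SD of 13.2.

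- Normal approximation: n per arm = 2 × (1.960 + 0.842)² × 13.2² / 7² = 55.8, so 56 per arm and 112 in total.
- t-test version: 56.8, so 57 per arm and 114 in total. This matches the plan.
- The pilot's baseline SD of 13.8 would give 124, and a one-sided test with SD 13.2 would give 88 to 90. Neither matches.
- Inflation: 114 × 1.10 = 125.4, so 126. This matches.

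I therefore use SD 13.2, two-sided 5% alpha, 57 evaluable per arm and 63 randomised per arm.

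**2. Size of the smaller centre.** 24 / (200 + 24) = 10.7%, and 0.107 × 126 = 13.5, so about 14 patients from Nantes.

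**3. Chance of an uneven split without stratification.** With 63 per arm and 14 Nantes patients, the number of Nantes patients in one arm is hypergeometric (126, 14, 63).

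- 10:4 or worse in either direction: 15%.
- 11:3 or worse: 4%.
- Simulated permuted blocks of 4 and 6 (block lengths assumed) give about 16% for 10:4 or worse, so blocking without strata does little to balance centre.
- Simple coin-toss allocation would give 2 × P(X ≥ 10 | 14, 0.5) = 18%, but the plan does not use it.

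**4. Shift in the contrast.** A 10:4 split is a between-arm difference in Nantes share of 6/63 = 9.5 percentage points. The shift is d × 6/63, where d is the centre difference in FIQR that remains after adjustment for the D0 score. The documents give no value for d, so I assume 3, 5 and 7 points. The standard error of the contrast is 13.2 × √(2/57) = 2.47.

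| d (assumed) | Shift at 10:4 | Share of the 7-point target | In standard errors |
|---|---|---|---|
| 3 | 0.29 | 4% | 0.12 |
| 5 | 0.48 | 7% | 0.19 |
| 7 | 0.67 | 10% | 0.27 |

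**5. Gain from a centre term.** With f = 14/126, the variance due to centre is f(1 − f)d². The within-centre SD is √(13.2² − f(1 − f)d²). Power at 57 per arm, by the normal approximation, is Φ(7/SE − 1.96).

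| d (assumed) | Variance removed | Within-centre SD | Power |
|---|---|---|---|
| no centre term | – | 13.20 | 80.8% |
| 3 | 0.5% | 13.17 | 81.0% |
| 5 | 1.4% | 13.11 | 81.4% |
| 7 | 2.8% | 13.02 | 81.9% |

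**6. Sensitivity to the intake split.** If Nantes supplied a third of the patients (42 of 126, an assumption), the 95th percentile of the gap in Nantes share would be 10/63 = 15.9 percentage points. The shift would be 0.48 to 1.11 points, and adjusted power 81.3% to 83.3%. The split among the three Vendée sites is not given, so a four-site version cannot be computed.

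**The case against.** The strongest reply is that nothing here is invalid. Under randomisation, chance imbalance is already covered by the standard error and by alpha, so leaving centre out biases nothing. That stands. The reply adds that the numbers are small, and they are: even 10:4 with a 5-point centre gap moves the estimate by about a fifth of a standard error. Common eligibility criteria, including an FIQR ceiling of 59, and adjustment for the D0 score leave less room for centre to matter. The centre gap is assumed throughout.

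Three stronger readings are tempting, and the documents do not support them.

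- A reader might infer that a single unstratified list is used. The singular wording and the entry fields point that way, but the text never says so. Login details could identify the site, and an online randomisation guide is mentioned that is not part of the documents. What can be said is that stratification is not described.
- A reader might infer that each centre supplies its own coaches. Institution physiotherapists give only 4 of the 9 experimental sessions. The association gives the other 5 and every control session, and section 4.3 says both professions are briefed in advance to coordinate care.
- A reader might conclude that a centre term deals with differences between coaches. It does not. Those differences arise in the experimental arm only, so they are a treatment-by-centre effect or one-arm clustering. Neither stratification nor a centre main effect corrects for them, and coaching is not a reason for this change.

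Nor do the documents contain any data showing that the two institutions recruit different patients. That is plausible, but it is not established.

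**Conclusion.** The point holds as a cheap improvement. As written, centre is not described as a stratification factor and appears in no model, so a chance imbalance would be neither prevented nor adjusted for. The consequence is a modest loss of precision. There is about a 15% chance of a Nantes split of 10:4 or worse, worth roughly 0.3 to 0.7 FIQR points against a 7-point target, and about 0.2 to 1.1 percentage points of power are forgone.

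These figures rest on the section 3.4 intake rates, an SD of 13.2 inferred from the sample size, 63 per arm, and an assumed residual centre gap of 3 to 7 points. A larger Nantes share would raise them, and a gap near zero would remove them. The case for acting is that adjustment costs almost nothing and settles the analysis before the data are seen. The sample size needs no change.

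**What to change.** 1. In section 5.2, add centre (CHD Vendée or CHU Nantes) as a prespecified fixed effect in the primary FIQR model and in the secondary mixed models. This is the main change, and it works whether or not recruitment has started. Two levels are suggested because section 4.2 defines the trial by two institutions and no intake is given for the individual Vendée sites.
2. State whether the randomisation list is stratified by centre. If it is not and recruitment has not begun, generate one list per institution, with block lengths that vary and are kept undisclosed. This is secondary to the model term.

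Cost: one degree of freedom in each model, and two lists in place of one in a system that is already web-based. The real downside is that block ends become slightly easier to guess at a centre with about 14 patients in an open trial. Varying, undisclosed block lengths reduce that risk but do not remove it. If differences between coaches are of interest, they need a separate sensitivity analysis with a centre-by-group term or coach-level clustering.
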